3.4.2 Inclusion criteria

Eligible patients must meet all of the following inclusion criteria:

- 1. Patients who completed study treatment at their regular Week 24 (EOT) Visit within the core study.
- 2. Women of childbearing potential must:
 - Have a negative urine pregnancy test at their regular Week 24 visit within the core study.
 - Use reliable methods of contraception for up to at least 30 days after study drug discontinuation as described in Section 4.4.2.
- 3. Signed informed consent for participating in the extension study prior to administration of the first dose in the transition period (i.e., prior to continuation of dosing at Visit 11 (Week 24) of the core study).

3.4.3 Exclusion criteria

Eligible patients must meet none of the following exclusion criteria:

- 1. Patients meeting at their regular Week 24 (EOT) Visit, during the transition period, and/or at Visit E1 any of the study-specific criteria for permanent discontinuation of study drug as defined in Appendix 1, or patients receiving any of the prohibited concomitant medication as outlined in Section 3.4.4.3 and Appendix 8.
- 2. Any other clinically relevant medical or surgical condition, which, in the opinion of the investigator, would put the patient at risk by participating in the extension study.

3.4.4 Concomitant medications

3.4.4.1 Recommended concomitant medications

Acute exacerbations of MS should be treated with methylprednisolone 1 g intravenously daily for 3 to 5 days. Oral taper with corticosteroids is not permitted.

3.4.4.2 Allowed concomitant medications

Administration of intravenous (i.v.) atropine in the event of symptomatic bradycardia.

Vaccination with non-live vaccines is allowed while on study treatment if the vaccination is advised by the primary investigator / treating neurologist, based on her/his clinical assessment of the risk/benefit for the individual patient, and if supported by guidelines for vaccination relevant to this patient population, as applicable.

Ponesimod / ACT-128800 / JNJ-67896153 Multiple Sclerosis		EudraCT 2009-011470-15 EDMS-ERI-206617631
Protocol AC-058B202	Confidential	
Version 12		
15 March 2022, page 63/179		

Patients receiving non-live vaccination against influenza or COVID-19 while on study treatment will have 5 mL of blood drawn prior to and at least 3 weeks after vaccination in order to explore changes in vaccine-specific antibody titers from pre- to post vaccination. Samples will be analyzed at the end of the study at the latest. In case of a vaccine requiring the administration of multiple doses, the post-vaccination sample should be collected at least 3 weeks after the administration of the last dose.

Glatiramer acetate and IFN β -1a are allowed only during study drug interruptions for planned pregnancy. These treatments may be started 7 days after study drug interruption and must be stopped 7 days before study drug re-initiation.

Low dose of corticosteroids (up to 10 mg of prednisone equivalent daily), given as shortterm treatment (up to 2 weeks per treatment cycle with at least 8 weeks' interval between treatment cycles and no more than 4 weeks per year of the study duration on average), and inhaled corticosteroids for pulmonary conditions.

Other treatments considered necessary for the patient's benefit and not categorized as prohibited concomitant medications.

3.4.4.3 Prohibited concomitant medications

- Systemic corticosteroids or adrenocorticotropic hormone (ACTH), except for: the treatment of acute MS exacerbations [see Section 3.4.4.1]; short-term treatment with a low dose of corticosteroid; and inhaled corticosteroids for pulmonary conditions [see Section 3.4.4.2].
- Immunomodulating treatment (e.g., IFN β , glatiramer acetate, natalizumab or other monoclonal antibody therapy [except glatiramer acetate or IFN β -1a during study drug interruptions for planned pregnancy as described under "Allowed"]).
- Immunosuppressive treatment (e.g., cladribine, mitoxantrone or other systemic immunosuppressive drugs such as azathioprine, cyclophosphamide, cyclosporine or methotrexate).
- i.v. immunoglobulin.
- Plasmapheresis, cytapheresis, or total lymphoid irradiation.
- Vaccination with live vaccines, except if performed during a temporary treatment interruption period. In this case it must be performed not earlier than 1 week after the last dose of study treatment, and treatment can be re-initiated only after at least 4 weeks from completion of vaccination.
- β-blockers, diltiazem, verapamil, digoxin, or any other anti-arrhythmic or HR -lowering systemic therapy [non-exhaustive list provided in Appendix 8] during the titration (i.e., during the first 14 days after re-initiation of study treatment). Treatment with any of these therapies is also not recommended during maintenance treatment with ponesimod (i.e., 20 mg) and should be considered with caution if an alternative medication cannot be used.

Ponesimod / ACT-128800 / JNJ-67896153 Multiple Sclerosis Protocol AC-058B202 Version 12 15 March 2022, page 64/179

Confidential

EudraCT 2009-011470-15 EDMS-ERI-206617631

- Medications with risk of torsades de pointes (TdP) should not be administered as ponesimod may potentially enhance their effect on QT interval unless the benefit-risk is acceptable, as judged by the investigator [non-exhaustive list provided in Appendix 9].
- Any investigational drug.

3.5 Study drugs

Study drug is ponesimod.

Note that the term "study drug" refers to study medication (ponesimod) provided by the sponsor, as opposed to "commercially available ponesimod" that may be started after discontinuation of study drug.

3.5.1 Ponesimod

During TP1:

Ponesimod was supplied as its free base in hard gelatin capsules formulated at strengths of 10, 20, and 40 mg.

During TP2:

Ponesimod was supplied as oral film-coated tablets formulated at strengths of 10 and 20 mg.

During TP3:

Ponesimod is supplied as oral film-coated tablets formulated at strength of 2, 3, 4, 5, 6, 7, 8, 9, 10, and 20 mg.

3.5.2 Study drug storage and dispensing

The investigator is responsible for safe and proper handling and storage of the study drug at the investigational site and for ensuring that the study drug is administered only to patients enrolled in the study and in accordance with the protocol.

Study drug must be kept in a locked room, which can be accessed only by the pharmacist, the investigator, or another duly designated person. The study drug must be stored according to the conditions specified on the medication labels. The study centers will be supplied with study drug according to the centers' needs depending on the number of patients entering the extension study. Each center will have an individual stock of study drug, which will be re-supplied continuously as soon as a predefined minimum level of study drug has been reached.

3.5.3 Study drug dosing scheme

One capsule (during TP1) or one tablet (during TP2 and TP3) of study drug will be administered orally o.d. in the morning, with or without breakfast (preferably always in the

Ponesimod / ACT-128800 / JNJ-67896153 Multiple Sclerosis		EudraCT 2009-011470-15 EDMS-ERI-206617631
Protocol AC-058B202	Confidential	
Version 12		
15 March 2022, page 65/179		

same way and at approximately the same time). On each day of the study visits, the administration of the study drug will only be done once PK trough level sampling and the following safety assessments are completed: BP, ECG, PFTs, laboratory tests, and urine pregnancy test.

Since this study was initially performed in a double-blind fashion during TP1 and TP2, all patients, notwithstanding whether they have been on placebo or ponesimod during the core study, needed to perform an uptitration scheme. For patients treated with ponesimod during the core study this was a mock uptitration. The treatment groups in the extension study will be as follows:

Patients who were on ponesimod in the core study continued on the same dose in the transition period and had mock dose titrations on Day 1 (Visit E1), Day 8 (Visit E2), and Day 15 (Visit E3):

- Group I: Group I in the core study (10 mg). 10 mg from Visit E1 (Day 1) until end of TP2. 20 mg during TP3 until EOT3.
- Group II: Group II in the core study (20 mg). 20 mg from Visit E1 (Day 1) until EOT3.
- Group III: Group III in the core study (40 mg).
 40 mg from Visit E1 (Day 1) until at least Visit E9 or up to E13 (EOT2).
 10 or 20 mg from Visit P1 until end of TP2.
 20 mg during TP3 until EOT3.

Patients who were on placebo (Group IV in the core study) continued on placebo in the transition period and then be randomized 1:1:1 to:

- Group IV: 10 mg from Day 1 (Visit E1) until end of TP2. Mock dose titrations on Day 8 (Visit E2) and Day 15 (Visit E3). 20 mg during TP3 until EOT3.
- Group V: 10 mg from Day 1 (Visit E1) to Day 7. 20 mg from Day 8 (Visit E2) until EOT3. Mock dose titration on Day 15 (Visit E3).
- Group VI: 10 mg from Day 1 (Visit E1) to Day 7. 20 mg from Day 8 (Visit E2) to Day 14. 40 mg from Day 15 (Visit E3) until at least Visit E9 or up to E13 (EOT2). 10 or 20 mg from Visit P1 until end of TP2. 20 mg during TP3 until EOT3.

EudraCT 2009-011470-15

EDMS-ERI-206617631

Ponesimod / ACT-128800 / JNJ-67896153 Multiple Sclerosis Protocol AC-058B202 Version 12 15 March 2022, page 66/179

Confidential

An overview of the titration scheme by treatment arm is provided in Table 5.

Table 5:	Ponesimod dose levels and uptitration scheme
----------	--

		Treatment groups					
						Ponesimo	d
	Core study:	Placebo			10 mg	20 mg	40 mg
			- +		¥	¥	¥
	Extension study:	10 mg	20 mg	40 mg	10 mg	20 mg	40 mg
Transition ¹	Day –3 to Day –1	0 mg	0 mg	0 mg	10 mg	20 mg	40 mg
Dose level 1 ⁴	Day 1 to Day 7	10 mg	10 mg	10 mg	10 mg ^{2,3}	20 mg ^{2,3}	40 mg ^{2,3}
Dose level 2 ⁴	Day 8 to Day 14	10 mg ²	20 mg	20 mg	10 mg ^{2,3}	20 mg ^{2,3}	40 mg ^{2,3}
Dose level 3 ⁴	Day 15 up to W96	10 mg ^{2,3}	20 mg ^{2,3}	40 mg ³	10 mg ^{2,3}	20 mg ^{2,3}	40 mg ^{2,3}
Dose level 4 ⁵	Day 1 up to	10 mg ³	20 mg ³	10/20 mg ³	10 mg ³	20 mg ³	10/20 mg ³
Dose level 5 ⁶	W540	20 mg ³	20 mg ³	20 mg ³	20 mg ³	20 mg ³	20 mg ³

¹ Transition dose core study maintenance dose.² Mock uptitrations. ³ Maintenance dose. ⁴ Treatment period 1. ⁵ Treatment period 2. ⁶ Treatment period 3.

3.5.4 Study drug up- and down-titration

Study drug up-titration other than described in this protocol is not allowed. Down-titration of study drug is not allowed.

3.6 Study drug discontinuation and study withdrawal

3.6.1 Study drug discontinuation

The investigator must permanently discontinue the study drug if continued administration of the study drug is believed to be contrary to the best interests of the patient.

The premature discontinuation of study drug might be triggered by an AE, a diagnostic or therapeutic procedure, an abnormal assessment (e.g., ECG, PFTs or laboratory abnormalities), or for administrative reasons, in particular withdrawal of the patient's consent.

In addition, study drug must be discontinued if any of the specific discontinuation criteria listed in Appendix 1 is met, including cardiac and pulmonary parameters, arterial hypertension, lymphocyte counts, infection, macular edema and pregnancy.

Heightened vigilance is required for opportunistic infections, particularly viral infections with neurological symptoms such as reactivation of human herpes viruses (herpes simplex

Ponesimod / ACT-128800 / JNJ-67896153 Multiple Sclerosis		EudraCT 2009-011470-15 EDMS-ERI-206617631
Protocol AC-058B202	Confidential	
Version 12		
15 March 2022, page 67/179		

viruses, varicella-zoster virus, Epstein-Barr virus, cytomegalovirus) and reactivation of John Cunningham virus (JCV) causing progressive multifocal leukoencephalopathy (PML). The patient must be instructed to contact the investigator immediately if symptoms of infection occur. In the event of an opportunistic infection, the study drug must be permanently discontinued [Appendix 3].

If for any reason a patient has to be treated with immunomodulators, immunosuppressants, immunoglobulins or investigational drugs, or has to undergo plasmapheresis, cytapheresis or total lymphoid irradiation, the study drug must be permanently discontinued.

Please refer to Section 3.6.2 and Appendix 5 for further guidance on re-initiation of the ponesimod in case of an interruption of the study drug.

3.6.2 Study drug interruption

Study drug interruption should be avoided.

If study drug intake is interrupted by the patient for any reason, she/he must immediately inform the primary investigator / treating neurologist.

Study drug may be temporarily interrupted in response to an AE, a diagnostic or therapeutic procedure, a laboratory abnormality, a planned pregnancy, or for administrative reasons. The permitted maximum duration of the study drug interruption is 81 weeks for planned pregnancies and 12 weeks for other reasons (if exceeded, the patient will then be prematurely discontinued from the study).

In the event of a re-initiation of study drug, one tablet of ponesimod 2, 3, 4, 5, 6, 7, 8, 9, or 10 mg will be taken orally o.d. during the uptitration period (Day 1 to 14). During the maintenance period, patients will continue to take one tablet of ponesimod 20 mg orally o.d. [Table 6]. If a blister kit with the starting dose of 2 mg is not available at the site, re-initiation should be delayed until it becomes available (temporary treatment interruption).

Detailed guidance on how to re-initiate study drug in the event of drug interruption is provided in Appendix 5.

EudraCT 2009-011470-15 EDMS-ERI-206617631

Ponesimod / ACT-128800 / JNJ-67896153 Multiple Sclerosis Protocol AC-058B202 Version 12 15 March 2022, page 68/179

Confidential

Treatment period	Duration	Dose regimen
Titration	Day 1 and 2	2 mg
Titration	Day 3 and 4	3 mg
Titration	Day 5 and 6	4 mg
Titration	Day 7	5 mg
Titration	Day 8	6 mg
Titration	Day 9	7 mg
Titration	Day 10	8 mg
Titration	Day 11	9 mg
Titration	Day 12 to 14*	10 mg
Maintenance	Day 15 until EOT3	20 mg

Table 6:2-week gradual uptitration regimen

* An additional visit 14 days (± 1 day) after the day of re initiation (Re initiation Day 15) is mandated for patients with cardiovascular risk factors [see Appendix 5], but may be scheduled for any patient at the discretion of the investigator / treating neurologist. The titration kit will therefore include 3 additional tablets (to be used if applicable) for treatment on Day 15 17 (i.e., dose regimen 20 mg).

EOT3 End of Treatment

3.6.3 Patients' follow-up after study drug discontinuation

All randomized patients who received the study drug (for any length of time) must perform all protocol-mandated assessments of the corresponding EOT visit at the time of premature study drug discontinuation, i.e., as soon as possible but no later than 5 days after the last dose of study drug. In addition, the corresponding Safety Follow-up visits must be performed.

• For TP1:

The corresponding EOT visit is EOT2.

In case of study drug discontinuation during or after completion of TP1, Follow-up Visit E1 and Follow-up visit E2 should be done 8 and 30 days respectively after the day of the last dose of study drug, regardless of the timing of the EOT2 visit.

• For TP2 and TP3:

The corresponding EOT visit is EOT3.

Follow-up visits 1, 2 and 3 should be done 8, 30, and 90 days, respectively, after the day of the last dose of study drug, regardless of the timing of the EOT3 visit.

Patients will follow the standard of care after completing the study.

Ponesimod / ACT-128800 / JNJ-67896153 Multiple Sclerosis		EudraCT 2009-011470-15 EDMS-ERI-206617631
Protocol AC-058B202	Confidential	
Version 12		
15 March 2022, page 69/179		

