3.12.3.5 EOT3 (Week 540)

The visit window for this visit is ± 14 days.

An EOT3 visit will be performed:

- For patients who complete Week 540 of TP3 according to the protocol: One day after the last dose of study drug
- For patients who complete TP2 according to the protocol but do not enroll into TP3: As soon as possible but no later than 5 days after the last dose of study drug
- For patients who discontinue study drug prematurely during TP2 or TP3: As soon as possible but no later than 5 days after the last dose of study drug

For patients completing study treatment due to availability of commercially available ponesimod, an EOT3 visit should be conducted as soon as possible, but no later than 5 days after the last dose of study drug. Commercially available ponesimod may be initiated on the day after last intake of study drug.

At EOT3 visit the following assessments must be performed:

- PFTs (FEV₁, FVC);
- Change in concomitant medication, if any;
- Physical examination (including careful skin examination);
- Ophthalmological examination (best corrected visual acuity, low contrast visual acuity, visual fields, and dilated ophthalmoscopy);
- 12-lead ECG and SBP/DBP (under the responsibility of the physician evaluating cardiac safety assessments or primary investigator / treating neurologist);
- Standard 2D/Doppler echocardiography (at selected centers);
- Laboratory tests (central laboratory) preferably under fasting conditions:
 - Hematology, blood chemistry, urinalysis;
 - Pregnancy test;
- EDSS and FS scores (assessed by the evaluating neurologist);
- MRI examination;
- Chest X-ray;
- Recording of AEs and SAEs.

When the patient has completed all scheduled assessments, Follow-up visit 1 will be scheduled 8 days after the last dose of study drug.

Ponesimod / ACT-128800 / JNJ-67896153		EudraCT 2009-011470-15
Multiple Sclerosis		EDMS-ERI-206617631
Protocol AC-058B202	Confidential	
Version 12		
15 March 2022 nage 104/179		

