3.12.4.2 Visit E15: EOT2 + 30 days (Follow-up visit E2)

The visit window for this visit is ± 5 days.

Thirty days after the last study drug administration, the following assessments must be performed:

- Change in concomitant medication, if any;
- Physical examination (including careful skin examination);
- PFTs (FEV₁, FVC);
- Ophthalmological examination (best corrected visual acuity, low contrast visual acuity, visual fields, and dilated ophthalmoscopy);
- Laboratory tests (central laboratory) in fasting condition:
 - Hematology, blood chemistry, urinalysis;
 - Pregnancy test;
- 12-lead ECG and SBP/DBP (under the responsibility of the physician evaluating cardiac safety assessments);
- EDSS and FS scores (assessed by the independent evaluating neurologist);
- MRI examination;
- Recording of AEs and SAEs.

Before discharge, WOCBP must be reminded that they must use the chosen methods of contraception until 30 days after the last study drug administration.

3.12.4.3 Follow-up visit 1 (FU1): 8 days after the last dose of study drug

The visit window for this visit is ± 1 day.

At this visit the following assessments must be performed:

- Change in concomitant medication, if any;
- Physical examination;
- PFTs (FEV₁, FVC);
- Laboratory tests (central laboratory) preferably under fasting conditions:
 - Hematology, blood chemistry, urinalysis;
- 12-lead ECG and SBP/DBP (under the responsibility of the physician evaluating cardiac safety assessments or primary investigator / treating neurologist);
- Recording of AEs and SAEs.

Ponesimod / ACT-128800 / JNJ-67896153 Multiple Sclerosis Protocol AC-058B202 Conf Version 12 15 March 2022, page 106/179

Confidential

EudraCT 2009-011470-15 EDMS-ERI-206617631

When the patient has completed all scheduled assessments, Follow-up visit 2 (FU2) will be scheduled 30 days after the last dose of study drug.

3.12.4.4 Follow-up visit 2 (FU2): 30 days after the last dose of study drug

The visit window for this visit is ± 5 days.

Thirty days after the last study drug administration, the following assessments must be performed:

- Change in concomitant medication, if any;
- Physical examination (including careful skin examination);
- PFTs (FEV₁, FVC);
- Ophthalmological examination (best corrected visual acuity, low contrast visual acuity, visual fields, and dilated ophthalmoscopy);
- Laboratory tests (central laboratory) preferably under fasting conditions:
 - Hematology, blood chemistry, urinalysis;
 - Pregnancy test;

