The primary investigator / treating neurologist or the study nurse must instruct/remind the patient to interrupt the contraception until after delivery and to follow all the visits scheduled as per protocol during the study drug interruption period and until the study drug has been re-initiated or permanently discontinued.

3.12.5.5 Additional unscheduled visit for eligibility assessment for re-initiation of study drug for female subjects who interrupted the study drug for planned pregnancy and who wish to re-initiate the study drug after delivery

As described in Appendix 1 section D, female patients who interrupted the study drug for planned pregnancy and who wish to re-initiate the study drug after delivery will need to be assessed for eligibility for study drug re-initiation. Unless the patient has been treated with a disease modifying therapy (DMT; IFN β -1a or glatiramer acetate) during the pregnancy and post-partum, this visit should take place as soon as possible after delivery in order to minimize the post-partum period without MS treatment. In addition, this visit should take place 30 (±5) days before the study drug re-initiation.

Ponesimod / ACT-128800 / JNJ-67896153 Multiple Sclerosis Protocol AC-058B202 Version 12 15 March 2022, page 111/179

Confidential

EudraCT 2009-011470-15 EDMS-ERI-206617631

During this visit, the following assessments must be performed before study drug administration:

Urine pregnancy test first and, if urine pregnancy test is negative:

- PFTs (FEV₁ and FVC);
- Laboratory tests (central laboratory) preferably under fasting conditions: Hematology, blood chemistry, urinalysis;
- Assessment of methods of contraception;
- Recording of changes in concomitant medication, if any;
- Body temperature;
- Body weight;
- Physical examination;
- 12-lead ECG and SBP/DBP (under the responsibility of the physician evaluating cardiac safety assessments or primary investigator / treating neurologist);
- EDSS and FS assessment (performed by the evaluating neurologist);
- MRI examination;
- Ophthalmological examination (best corrected visual acuity, low contrast visual acuity testing, visual fields, and dilated ophthalmoscopy; OCT in case of suspected clinically significant findings [e.g., macular edema]);
- Recording of AEs and SAEs;
- Remind the patient to use the methods of contraception defined for this study. The reminders must be documented in the hospital chart;

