If a patient becomes pregnant while on study drug, study drug must be immediately and permanently discontinued. The investigator must counsel the patient and discuss the risks of continuing with the pregnancy and the possible effects on the fetus.

Planned pregnancy:

Female patients participating in the study and wishing to become pregnant during the study may stay in the study and will have the study drug interrupted prior to pregnancy and reinitiated after delivery.

Before becoming pregnant, the following protocol requirements must be met:

- The wish to become pregnant and stay in the study has to be communicated by the female patient to the primary investigator / treating neurologist during a scheduled visit occurring no later than at Visit P28 (Week 324). If the wish to become pregnant is communicated after Visit P28 (Week 324), the study drug interruption for a planned pregnancy would not be allowed.
- Prior to interrupting contraception, the patient must have 2 negative urine pregnancy tests: one at the scheduled visit on the day of study drug interruption and one 30 days after study drug interruption.
- The total duration of the study drug interruption due to planned pregnancy must not exceed 81 weeks, otherwise the study drug will be discontinued.
- The patient must agree to be followed by an appropriate health care professional (e.g., gynecologist, obstetrician and/or midwife) during pregnancy according to local practice, to have the reports from pregnancy assessments communicated to the primary investigator / treating neurologist and to have the information on the patient's MS status communicated by the primary investigator / treating neurologist to that health care professional.

In addition to the protocol requirements above, the primary investigator / treating neurologist must explain the following to the patient:

- The potential impact of pregnancy and post-partum period on the patient's MS and potential medical treatments that would be available for the patient while the study drug is interrupted;
- Re-initiation of study drug can only take place after delivery and after breastfeeding has been stopped, if applicable, and will require a medical evaluation of patient's eligibility for study drug re-initiation;
- Timing of the interruption and possible re-initiation of study drug and of contraception, related pregnancy tests and unscheduled visits;
- The need for re-uptitration at the study drug re-initiation;

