• The need to follow the visit schedule as per protocol during pregnancy including all the scheduled assessments and procedures except MRI, PFTs and without study drug dispensing.

The re-initiation of study drug after delivery requires the following eligibility criteria:

- The patient has completely stopped breastfeeding prior to re-initiation of the study drug;
- The patient must have been using the reliable methods of contraception as described in Section 4.4 for at least 30 days prior to re-initiation of study drug;
- The patient must have had 2 negative urine pregnancy tests performed 30 days apart; the second one must be during the re-initiation visit;
- The patient did/does not fulfill any protocol criteria for permanent study treatment discontinuation per Appendix 1 at any of the previous visits or at the unscheduled visit for re-initiation of the study drug except the planned pregnancy;
- In case the patient received another DMT (IFN β -1a or glatiramer acetate) during pregnancy and post-partum, this treatment must be discontinued at least 7 days before study drug re-initiation.

If the patient agrees to all of the above, the study drug will be interrupted at the scheduled visit once the patient, after having received the above explanation from the primary investigator / treating neurologist, has confirmed the wish to become pregnant and interrupt and potentially re-initiate the study drug. The sponsor has to be contacted in each particular case to confirm that the patient who wishes to become pregnant can continue in the study.

The above requirements for re-initiation of study drug after delivery apply to all cases of study drug interruption for planned pregnancy, irrespective of the duration of pregnancy and also to all cases where planned pregnancy did not occur but where the contraception was interrupted for any duration and the patient wishes to re-initiate the study drug.

E) Ocular abnormalities

In the event of suspected clinically significant findings (e.g., macular edema), an unscheduled ophthalmological assessment with OCT should be performed. In case of macular edema confirmed by the local ophthalmologist, the subject must permanently discontinue study treatment. Macular edema is to be managed and followed up until resolution. Any clinically relevant finding meeting the definition of an AE will be recorded accordingly in the eCRF.

Ponesimod / ACT-128800 / JNJ-67896153		EudraCT 2009-011470-15
Multiple Sclerosis		EDMS-ERI-206617631

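### A woman who becomes pregnant on study drug in TP2 or TP3 must have up to two routine gadolinium MRIs, because the MRI waiver covers planned pregnancy only

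*Protocol*

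**What the plan says.** Appendix 1 D of the protocol states: "If a patient becomes pregnant while on study drug, study drug must be immediately and permanently discontinued". Sections 3.6.1 and 4.4 agree.

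For discontinuation, Section 3.6.3 says that all randomized patients who took study drug "must perform all protocol-mandated assessments of the corresponding EOT visit at the time of premature study drug discontinuation", no later than 5 days after the last dose. The safety follow-up visits are also compulsory. In TP2 and TP3 these are EOT3, FU1, FU2 and FU3.

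Section 3.12.3.5 opens its list with "At EOT3 visit the following assessments must be performed" and includes both a pregnancy test and MRI. Section 3.12.4.4 (FU2) opens with "Thirty days after the last study drug administration, the following assessments must be performed" and again includes both. Neither list puts the test before the scan. Section 3.11.1.1 describes T1 imaging before and after intravenous gadolinium and schedules MRI at EOT3 and FU2.

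Under planned pregnancy, Appendix 1 D keeps the visit schedule "during pregnancy including all the scheduled assessments and procedures except MRI, PFTs and without study drug dispensing". That route requires the drug to be stopped before conception, and it has a cut-off: if the wish is "communicated after Visit P28 (Week 324), the study drug interruption for a planned pregnancy would not be allowed".

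**The concern.** The sponsor considered which assessments a pregnant participant should have and took MRI out, but wrote this only for women who planned the pregnancy. A woman who conceives on drug falls under Section 3.6.3, which is universal and uses *must*. The provisions written for her (Section 4.4 on counselling, Section 4.4.3 on reporting, Section 4.4.4 on following the pregnancy to its conclusion) adjust no assessment.

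A site that follows the text literally would book a contrast MRI for a patient it knows to be pregnant. A site that omits the scan departs from a stated obligation. Patient protection and consistency between sites are at stake, not the efficacy conclusions.

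**Working it through.** No sample size or error rate is involved, and the protocol states no total to reproduce. The check is a count of the listed assessments, a comparison of the two pregnancy routes, and some date arithmetic.

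**1. Count after premature discontinuation in TP2/TP3** (Sections 3.12.3.5, 3.12.4.3 to 3.12.4.5, 3.11.1.1 and Table 3)

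| Visit | Days after last dose | Pregnancy test | MRI |
|---|---|---|---|
| EOT3 | at most 5 | yes | yes |
| FU1 | 8 ± 1 | no | no |
| FU2 | 30 ± 5 | yes | yes |
| FU3 | 90 ± 7 | no | no |

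Routine MRIs = 1 (EOT3) + 1 (FU2) = 2. This is a maximum, because the FU2 scan falls in pregnancy only if the pregnancy is still ongoing then.

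**2. The two routes side by side**

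- *Planned pregnancy.* Section 3.12.5.4 schedules an MRI 30 days after interruption, at a visit where the pregnancy test must be negative before contraception stops. During pregnancy MRI is waived (Appendix 1 D). After delivery, the eligibility visit in Section 3.12.5.5 includes MRI in a list that begins "Urine pregnancy test first and, if urine pregnancy test is negative".
- *Pregnancy on drug.* Up to 2 MRIs while known to be pregnant, with no waiver and no stated order of test and scan.

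The planned route is therefore not free of scans. The difference is confined to scans during a known pregnancy.

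**3. When the scans would fall.** Suppose a scheduled 12-weekly test finds the pregnancy and dosing stops at once. The longest gap between scheduled tests is 84 + 14 + 14 = 112 days.

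- EOT3 is at most 112 + 5 = 117 days (16.7 weeks) after the last negative test.
- FU2 is at most 112 + 35 = 147 days (21.0 weeks) after it.

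Both scans can therefore fall within a continuing pregnancy.

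**4. Whether the planned route is still open under Version 12 (15 March 2022).** The request must be made by Week 324. Actual P1 dates are not given, so the ends of the range are assumed.

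- Latest P1: last first visit on 30 June 2011 (end of Q2 2011) + 96 weeks = 2 May 2013; + 3 months = 2 August 2013. Week 324 is then 18 October 2019, and 15 March 2022 is Week 449.6. Remaining treatment: 540 − 449.6 = 90.4 weeks.
- Earliest P1: 16 February 2012, the date of the amendment that introduced TP2. 15 March 2022 is then Week 525.7. Remaining treatment: 540 − 525.7 = 14.3 weeks.

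On these dates everyone still on treatment had passed Week 324, so any new pregnancy would fall under the rule without the exception. The same dates show nobody left in TP1, so the TP1 lists need no edit.

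**The case against.** The strongest reply has four parts.

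- **General safeguards exist.** Section 6.1.1 lets an investigator make an immediate change for safety reasons. Section 6.2.1 binds sites to GCP and the Declaration of Helsinki, and Section 6.2.3 lets patients withdraw freely. Scans follow a separate MRI Technology Manual (Section 3.3.5), a natural place for pregnancy screening. This lowers the practical risk. But none of these is a pregnancy exception in the protocol, and the manual could not be checked.
- **The waiver's reason is not given.** This stands. A reader might infer that the sponsor judged gadolinium unsafe in pregnancy, but the documents do not say so.
- **The two groups differ.** This also stands. A woman on the planned route already has an MRI and a lung-function test 30 days off drug (Section 3.12.5.4); a woman who conceives on drug has neither. A reader might infer from the wording of Appendix 1 D that PFTs at EOT3 and FU1 to FU3 should be waived too. The documents do not support that. Section 1.3.2.4 reports FEV1 falls that returned to baseline off drug, Appendix 1 C acts on measured falls below 80% of baseline, and SAP Section 5.4.5.5 summarizes follow-up values. These tests check recovery, and no reason is given to drop them.
- **Cost against benefit.** Cases should be few because contraception is mandatory (Section 4.4.2). Under Section 6.1.1 a change to assessments needs a substantial amendment, here across 81 centers in 21 countries. This argues for bundling the change, not for leaving the gap.

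**Conclusion.** The gap is real and minor. The protocol text requires up to 2 routine gadolinium MRIs (EOT3, and FU2 if the pregnancy is ongoing at about day 30) in a woman who becomes pregnant on drug in TP2 or TP3, although the sponsor removed MRI during planned pregnancy.

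A reader might call the two rules contradictory. They are not, since they cover different women; this is an omission. Nor does the sponsor's waiver support dropping the EOT3 chest X-ray, which it does not name.

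The count rests only on the protocol's own lists. The claim that the planned route has closed rests on planned dates and the assumed P1 range. The number of affected patients is not given. The conclusion concerns the protocol text only, since the MRI manual and consent pages were not seen.

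**What to change.** Add to Section 3.6.3 and Appendix 1 D, with a footnote to Table 3: *For any patient known to be pregnant at the visit, planned or not, routine protocol-scheduled MRI with gadolinium at EOT3 and FU2 is omitted unless clinically indicated (e.g., suspected PML, Appendix 3). At EOT3 and FU2 the pregnancy test is read before MRI.*

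Keep the PFTs at EOT3 and FU1 to FU3, and leave the chest X-ray as it is.

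The cost is up to 2 missing scans per affected patient in a study whose endpoints are all exploratory, and two sentences and a footnote in a substantial amendment, which can wait for the next one. No SAP change is needed. SAP Section 6.4 excludes nobody for a protocol deviation, and the CUAL model in Section 5.3.4.3 takes its offset from the last scan at which T2 was measured, so a missing final scan shortens that patient's observation time.
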